Study Design: This study will undertake: (a) the collection of retrospective waste plasma/serum samples from Covid-19 positive patients and extract from existing nasopharyngeal swabs and (b) the recruitment of Covid-19 positive hospitalised and non-

hospitalised and nursing home patients, hospital and nursing home staff, for whole genome sequencing, human host genomic analyses and viral genomic analyses. This research study will take place across three trust areas in Northern Ireland and will be conducted simultaneously in four phases, namely:

Phase 1- Rapid access of waste serum/plasma samples from hospital laboratories

Phase 2- Rapid access of nasopharyngeal swab extract, collected from patients, NHS and nursing home staff and members of the public.

Phase 3- Recruitment of SARS-CoV-2 patients who have tested positive by virus PCR assay from both hospitals and trust affiliated nursing homes and community.

Phase 4- Recruitment of hospital-tested and nursing home staff

Recruitment of participants and sample collection

Rapid Access to retrospective samples from hospital laboratories:

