-Rapid access will be also be sought across the three trusts for extract from the nasopharyngeal swabs collected from patients, NHS and nursing home staff and members of the public throughout the three Trust areas (these swabs will have already tested COVID-19 positive or negative and results acted upon).The extract will undergo viral genome analysis. 16S microbiome analysis will also be carried out on a selected COVID positive subset with matching controls to correlate microbiome with severity. Up to 500 sample whole genome sequencing and other genomic analyses will be performed. Again, as these samples will be collected retrospectively, it would be imperative to follow up with a subset of these participants (~ n = 500) at three, six and 12 months and ask them to provide a saliva sample, 30ml plasma sample to check if a) The antibody persists and b) to extract DNA (which is not readily available in the swab extract) and provide a saliva sample (~4ml). In addition, one set of five 20ul dried blood spots will also be collected and a lateral flow assay for COVID-19 antibodies performed at recruitment and at each timepoint. NICRN/research nurses based at each trust will initially liaise with the custodians of the extract to follow up with those patients, for those who are contactable (recovered and discharged from hospital, didn't need hospitalisation or tested negative) the nurses will post out a, pre-packed, PIS and invitation letter (appendix 4) about this research, a consent form (appendix 5) and a stamped addressed return envelope. Those that are interested can call the researchers to find out more and if still interested post back the consent form in the pre addressed envelope, the researchers will then follow up. For those patients who are hospitalised or in a nursing home a member of the clinical care team can discuss the study with the patient and if they are interested, get verbal permission for the researchers to give them a PIS (appendix 4). For those who wish to participate, they can contact the researcher whose details are on the PIS. Informed written consent (appendix 5) will be obtained prior to enrolment on study. In the case of those ALC, and where a family member is not available to act as a nominated responsible person, the research team in conjunction with the PI will

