Hospital and nursing home staff recruitment: All HSC employees aged 18 years and over, employed within facilities at the WHSCT, BHSCT and the SHSCT and trust affiliated nursing homes within the trust areas (n = 500) are eligible to participate in this research. Trust/nursing home wide emails with an attached PIS explaining the study (appendix 6) will be sent to all staff. In addition, information regarding the research will be put on Trust and Nursing home websites and social media platforms e.g. Facebook and Twitter. Posters (appendix 8) will also be placed in communal areas ensuring information can be accessed by everyone. Staff will be directed to the researchers on the study via email or phone to discuss the study in more detail. For those who still wish to participate and who meet the inclusion criteria, written informed consent (appendix 7) will be obtained by the researcher(s).

Sample Collection: Once informed consent has been obtained each participant will provide (i) one 30 ml whole blood sample, one set of dried blood spots (DBS) and a saliva sample (~4ml) at recruitment. Then, only if SARS-CoV-2 symptoms such as a high temperature/a

new continuous cough <https://www.nhs.uk/conditions/coronavirus-covid-19/check-if-you-have-coronavirus-symptoms/> experienced during 2 week post recruitment period: (ii) a saliva sample, one 30 ml whole blood sample and one set of dried blood spots (DBS) and a lateral flow assay for COVID-19 antibodies performed (between 0 and 10 days of symptom onset), (iii) a saliva sample, one 30 ml whole blood sample and one set of DBS and a lateral flow assay for COVID-19 antibodies performed between 14-28 days after symptom onset (iii) a saliva sample, one extra set of 30ml whole blood and DBS to be taken only if pneumonia occurs during (usually only in severe symptom cases) (iv) In addition, where possible sample will also be collected at 3 months, 6 months and 12 months of symptom onset. Sample collections will take place at an agreed convenient time and place.

Data Collection for all cohorts:

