Whole blood samples and swab extract will undergo viral genome analyses sequencing, transcriptomics, epigenetics, single nucleotide polymorphism (SNP) genotyping, WGS and RNAseq generation. Sample analysis will be performed at NICSM by the researchers or by a third party such as the virology laboratories at Queens University Belfast (QUB), Regional Virus Laboratory Belfast (RVL), Olink® proteomics (Uppsala, Sweden) or Genomics Medicine Ireland (GMI, Dublin, Dublin). This will require aliquots of plasma/serum or DNA to be transferred to the approved third party proteomic or genomic or service providers (such as QUB, Olink or GMI). In this event, all samples will be pseudo-anonymised. The codes relating to participant identification will not be disclosed to this study partner and remain in the custody of the chief investigator. Third party providers have already been approved as service providers with satisfactory evidence of encryption in storage and transfer of data and appropriate Material Transfer, Confidentiality and Intellectual Property agreements signed off by both the third party and the University. Unused DNA or plasma which is analysed by a third party such as GMI or Olink® proteomics will be destroyed. The research organisations that will use samples or data derived from analysis of samples could be not-for-profit e.g. universities or for-profit commercial companies (such GMI). GMI, however, have agreed to undertake: SNP genotyping, WGS and RNAseq generation analysis at no cost. Participant's name, address and personal details will not be made available to any organisation beyond the study team

Inclusion criteria

All cohorts:

- Gender: Male and female
- Age: >18
- BMI: Any
- Ethnic origin: Any

Hospitalised, non-hospitalised and nursing home patients:

- Symptomatic/non-Symptomatic patients testing positive or suspected of being positive for COVID-19/SARS-CoV-2 by virus PCR assay
- Nursing homes caring for elderly residents
- COVID-19 wards of participating hospitals

Hospital and nursing home staff:

- Any member of hospital or nursing home staff are eligible to participate whether they have ever tested positive or not for COVID-19/SARS-CoV-2 by virus PCR assay even if non-symptomatic.

Exclusion Criteria***All cohorts:***

- Under 18 years of age
- Those with intellectual disabilities or mental health illness

Blood sample collection

All venous blood samples will be taken by a trained phlebotomist or member of the research clinical team.

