When the participants agree to take part in a research study, the information about their health and care may be provided to researchers running other research studies in this organisation and in other organisations. These organisations may be universities, NHS organisations or companies involved in health and care research in this country or abroad. Participants' information will only be used by organisations and researchers to conduct research in accordance with the UK Policy Framework for Health and Social Care Research. This information will not identify the participants and will not be combined with other information in a way that could identify the participants. The information will only be used for the purpose of health and care research, and cannot be used to contact the participants or to affect their care. It will not be used to make decisions about future services available to the participants, such as insurance.

Statistical Analysis

A statistical sample size calculation was based on the core objective of measuring SARS-CoV-2 infection prevalence in specified populations: at community level (nursing home), in hospitalised SARS-CoV-2 positive cases and in frontline healthcare staff. If the true

prevalence of COVID-19 in frontline staff is 0.20 (20%), with a sample size of $n = 246$ we are 95% confident that our estimate will not be more than 5% (desired precision) below or above the true prevalence (20%). If we add 20% contingency in sample size for loss of follow up or drop out, we estimate that $n = 295$ frontline staff from each setting would be required. In another scenario, If the true prevalence of COVID-19 in hospitalized patients and nursing home residents is 0.60 (60%), with a sample size of $n = 369$ we are 95% confident that our estimate will not be more than 5% below or above the true prevalence (60%). Again, allowing for 20% contingency, we estimate that $n = 443$ patients from either setting are required.

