For the remaining core objectives, a predictive model would be built and tested for the severity of COVID-19 in infected individuals. Multi-predictor variable regression modelling would be the appropriate technique to achieve these. Disease severity will be the primary dependent variable of interest, with age, comorbidity, gender, immune response measure, viral strain, and host genetics as candidate predictor variables, although some of them may turn out to be non-significant predictors. Therefore, we anticipate 5-predictor models to be constructed from the dataset. Based on the Guideline of TRIPOD on the EPV (events per predictor variable), we used the following to determine the appropriate samples size i.e. 4 levels of severity measure X 20 events per predictor X 5 predictors = 400. Allowing for some loss of sample due to follow up we estimate that recruiting a sample of $n=500$ total infected individuals from both settings is sufficient for our study. The 20 EPV is considered to be a small to medium dataset and it is well above the minimum 10 EPV recommended for building predictive models.

Standard approaches will be used to detect patterns in missing data. Data will be modelled using bespoke packages (such as DADA2 for 16S rRNA, or RnBeads for epigenetics) in R, or using approaches in Galaxy, tools from Bioconductor or similar. Data exploration approaches such as PCA and hierarchical clustering will be used to look for trends and possible confounders in the data. Post-treatment outcome data will be summarised both in graphical and tabular form for each metric. Patients will be assigned non-response or good response status based on primary outcome measures. The data will be analysed to examine any relationships between host/viral genomic data, OLINK, CRP, flow cytometry immune cell data and outcome measures. Other established statistical hypothesis testing methods, including t-tests, ANOVA, linear models, or non-parametric tests depending on the distributions of the measures observed will be used to analyse secondary outcomes

References

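### The sample-size section requires 295 frontline staff per setting, but the staff recruitment target is 500 in total; two settings would need 590, and the protocol does not reconcile the figures

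*Protocol*

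**What the plan says.** Under Statistical Analysis, the first sample-size paragraph takes a staff prevalence of 20% and a desired precision of 5 points with 95% confidence. It arrives at 246, and after a 20% allowance for loss it states that 295 "frontline staff from each setting would be required".

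The section on hospital and nursing home staff recruitment gives one number for the whole staff cohort. HSC employees in facilities of the three trusts, together with those in "trust affiliated nursing homes within the trust areas (n = 500) are eligible to participate in this research". It sets no split between hospital and nursing home staff.

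Other places bear on what *setting* means:

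- Study Design describes Phase 4 as "Recruitment of hospital-tested and nursing home staff".
- The staff inclusion criterion reads "Any member of hospital or nursing home staff are eligible to participate".
- The later paragraph on the severity model refers to 500 "total infected individuals from both settings is sufficient for our study". That sentence is about infected individuals, so it is only indirect support for counting two settings.

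A second route could bring in staff. The Phase 2 swabs are "collected from patients, NHS and nursing home staff and members of the public throughout the three Trust areas", and the plan is to "follow up with a subset of these participants (~ n = 500) at three, six and 12 months".

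**The concern.** The protocol fixes two staff numbers that do not agree. *Each* implies at least two settings, so the stated requirement is at least 590, while the recruitment target is 500. The word *setting* is never defined for staff, and 500 is not derived anywhere as a staff figure.

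Prevalence is the objective on which this sample size is based. As written, a recruiting team cannot tell whether the requirement is 500 in total or 295 per setting, and nobody can say afterwards whether the planned precision was reached. Staff are recruited openly, by email, websites, social media and posters, with no quota. The smaller setting could therefore fall well below the size that the stated precision needs.

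**Working it through.** **Inputs.** From Statistical Analysis: prevalence p = 0.20, half-width d = 0.05, 95% confidence (z = 1.96), contingency 20%. From the staff recruitment section: total staff target 500.

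**The protocol's own figures reproduce.**

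- n = z² p(1 − p) / d² = 1.96² × 0.20 × 0.80 / 0.05² = 245.9, rounded up to 246.
- 246 × 1.2 = 295.2, stated as 295.

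**Requirement against target.**

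- Two settings (hospital, nursing home): 2 × 295 = 590, and 590 − 500 = 90 short.
- Without contingency: 2 × 246 = 492, which 500 covers. The contingency left is 500 / 492 = 1.016, that is 1.6%.
- If *setting* meant each of the three trusts: 3 × 295 = 885, a wider gap.
- If one pooled staff group was meant: 295 is enough and 500 exceeds it, but then the per-setting wording is wrong.

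**Precision that 500 delivers.** Half-width = 1.96 × √(0.20 × 0.80 / n). The planned loss is applied in two ways, as division by 1.2 (the protocol's own method) and as multiplication by 0.8.

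| Case | Before loss | After loss (÷ 1.2) | After loss (× 0.8) |
|---|---|---|---|
| All staff pooled | n = 500: ±3.51 | n = 417: ±3.84 | n = 400: ±3.92 |
| Each of two equal settings | n = 250: ±4.96 | n = 208: ±5.44 | n = 200: ±5.54 |

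**Unequal settings.** The protocol gives no split, so these sizes are assumptions. Before loss, a smaller setting of 200 gives ±5.5 points, 150 gives ±6.4 and 100 gives ±7.8.

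**Phase 2 route.** The number of staff in the follow-up subset of about 500 is not given, and the protocol does not say whether they count towards the prevalence estimate. This route therefore cannot be used to close the gap.

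**The case against.** The best defence is that a pooled estimate was intended. The sentence that opens the sample-size paragraph, like core objective (a), lists frontline healthcare staff as one population, and no objective asks for staff prevalence by workplace. On that reading 500 is ample. The reference to both settings in the severity-model paragraph most plainly concerns patients. These points are fair, and they mean that the size of the shortfall, 90, depends on the two-setting reading. They do not remove the contradiction: under the pooled reading the per-setting requirement is itself the error.

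A second point is that little precision is lost. The contingency is for drop-out, whereas staff give blood at recruitment, so a baseline estimate should lose little. With equal settings, ±5 points is then met at 4.96. This stands. The after-loss figures matter only if the protocol's own loss allowance is taken at face value.

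Third, the unequal splits are illustrations and not protocol figures. That is also correct. They show only what the absence of a split leaves open.

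Finally, 500 is the Phase 4 target, so a shortfall over all routes is not shown. The point is accordingly limited to Phase 4.

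**Conclusion.** The concern holds. The protocol states a per-setting staff requirement that its Phase 4 target does not meet on the natural reading of two settings: 590 required against 500 planned. No reading makes both statements correct together.

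The consequence is modest. At 20% prevalence and with equal settings, the target meets the stated precision before loss and misses it by about half a point after the planned loss; pooled precision is comfortably inside 5 points. The practical weakness is that, with no split set, ±5 points is not secured in the smaller setting. It should be fixed because the two figures are fixed in the protocol, conflict, and are easy to reconcile.

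**What to change.** Define *setting* for staff and reconcile 295 per setting with the target of 500. The sponsor may change either figure. A route that needs no extra enrolment is to keep 500, name it as the Phase 4 staff target, and replace the sentence requiring 295 per setting with text such as:

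> With the Phase 4 target of 500 staff, the 95% half-width at 20% prevalence is about 3.5 points pooled (3.8 to 3.9 after the planned loss) and about 5.0 points per setting if hospital and nursing home staff are equal in number (5.4 to 5.5 after the planned loss); it is wider in the smaller setting if they are unequal.

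Also state whether staff consented through the Phase 2 swab route count towards the prevalence estimate.

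A related wording query can be settled in the same edit. The patient requirement of 443 "patients from either setting are required" can mean each setting (2 × 443 = 886, above the 700 in the patient recruitment section) or both combined (within 700). Say which, and say whether the non-hospitalised patients among the 700 count. No new patient half-widths are proposed, because these patients are enrolled as positive or suspected positive.

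The cost is two or three sentences in the sample-size paragraph. On the route shown there is no additional enrolment, no quota and no change to the targets.

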COVID-19 positive/ SARS-CoV-2 inpatients and non-hospitalised patients (n = 700) aged 18 years and over tested at the WHSCT, BHSCT and SHSCT and have been admitted to COVID-19/ SARS-CoV-2 hospital wards (including from the Intensive Care Units) or out-patient and residents of trust affiliated nursing homes will initially be approached by their clinician, senior nurse or an NICRN research nurse. They will speak to the patient(s) about the study and if the patient is interested, verbal consent will be gained for the researcher to follow up with a Participant Information sheet (PIS) (appendix 6). Those interested patients fulfilling the inclusion criteria can then speak directly face to face (whereby the nurse will arrange a convenient time for researcher to visit the patient) to the researchers, the study will be discussed in detail and any issues will be addressed. If they are still interested in participating, written informed consent (appendix 7) will be obtained from the patient by the researcher(s) prior to enrolment on the study.

In the case of those ALC, and where a family member is not available to act as a nominated person the research team in conjunction with the PI will identify a nominated person who is unrelated to the conduct of the research and willing to provide a declaration for this study. The nominated person will always be a member of the nursing staff or the management team and part of the wider multi-disciplinary team within the hospital ward or nursing home facility of the individual lacking capacity. They (the nominated person) will also be provided

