with an invitation letter and PIS (appendix 13) and any queries answered, the nominated person can then contact the research team if they think the potential participant would have been interested in this research. The potential participant will not be enrolled on the study until full informed consent (appendix 14) has been given by the nominated person. This will still apply at all time points for those individuals who are unlikely to regain capacity and for those patients in hospital who are sedated/ventilated due to their COVID-19 symptoms, who may regain capacity. For those patients, capacity will always be assessed by a member of their direct clinical care team, the nurse in charge/manager in the nursing home and the PI at each hospital site who will be the consultant on or linked to the COVID ward (**The person assessing capacity will be recorded at all time points and a record kept**). For those that regain capacity during the duration of this research they will be given participant information sheet (appendix 4) to read for themselves and their consent (appendix 5) will be sought if they wish to proceed with the study. If they do not wish to continue, they will be given the option for any samples and data to be withdrawn and destroyed.

Sample Collection: Once informed consent has been obtained each participant will provide (i) one 30 ml whole blood sample, a saliva sample (~4ml) and one set of up to five 20ul dried blood spots (DBS; equivalent to five finger lancet blood droplets) and a lateral flow assay for COVID-19 antibodies performed at recruitment (between 0 and 10 days of symptom onset), (ii) again between 14-28 days after symptom onset (iii) again samples will be collected only if pneumonia occurs during episode (usually only in severe symptom cases) (iv) In addition, where possible samples will be collected at post 3 months, 6 months, 12 months and 18 months post symptom onset, the latter sample collections will take place at an agreed convenient time and place.

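### The severity model may use an immune measure taken after severe disease is established, because patients already in intensive care or ventilated are enrolled and counted towards it

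*Protocol*

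**What the plan says.** In the protocol's Statistical Analysis section, the second part of the plan is that "a predictive model would be built and tested for the severity of COVID-19 in infected individuals". The outcome is fixed: "Disease severity will be the primary dependent variable of interest". The model is to be built "with age, comorbidity, gender, immune response measure, viral strain, and host genetics as candidate predictor variables". No sampling time is attached to the immune measure and no assessment time to severity. The size is 4 severity levels × 20 events per predictor × 5 predictors = 400, raised to 500 infected individuals to allow for loss.

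Under Hospital and nursing home patient recruitment, eligible patients include those "admitted to COVID-19/ SARS-CoV-2 hospital wards (including from the Intensive Care Units". The consent arrangements there also cover "patients in hospital who are sedated/ventilated due to their COVID-19 symptoms", who may be enrolled through a nominated person.

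The Sample Collection paragraph for patients gives three sampling points in the acute phase:
- a first set "performed at recruitment (between 0 and 10 days of symptom onset";
- a second set, "again between 14-28 days after symptom onset";
- a conditional set: "again samples will be collected only if pneumonia occurs during episode".

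The two scheduled acute samples are timed from symptom onset. Neither is tied to the severity level the patient has reached.

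**The concern.** A predictive model needs predictors known before the outcome. Age, gender and host genetics meet that condition whenever they are recorded. An immune response measure need not, because severe illness can itself change inflammatory and cellular markers. In a patient first bled in intensive care or on a ventilator, the marker may describe a state already reached.

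If such patients enter the model on the same footing as patients sampled early, the immune measure can appear to discriminate between severity levels without any ability to forecast them. Its apparent usefulness for recognising patients who will deteriorate would then be overstated. The planned 500 would also include patients who cannot inform a prediction of reaching the top level, since they are there when first sampled.

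**Working it through.** **The plan's own figure.** 4 × 20 × 5 = 400, which is 100 per severity level. 400 / (1 − 0.20) = 500, so 500 implies a 20% loss; the section states no loss rate for this model. The figure reproduces. The point concerns the order of predictor and outcome in time, not this arithmetic.

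**Order in time.**
1. Enrolment is open to patients already in intensive care or ventilated.
2. Their first study sample is the recruitment sample, within 10 days of symptom onset.
3. That window does not prevent the severe level from being reached before the sample.
4. So even the natural choice of predictor, the recruitment sample, can follow the outcome. The 14–28 day sample is more exposed to this.

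**Illustration, two outcome groups.** All inputs are assumed: the marker has no true predictive value (AUC 0.50); it rises by d SD once severe disease is established; a share f of severe patients is first sampled after that point.
- Fully late sampling: AUC = Φ(d/√2). For d = 0.5, 1 and 1.5 this is 0.638, 0.760 and 0.856.
- Mixed sampling: AUC = 0.5 × (1 − f) + f × Φ(d/√2). With d = 1 and f = 0.5: 0.25 + 0.5 × 0.760 = 0.63. With f = 0.25: 0.375 + 0.25 × 0.760 = 0.565.

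**Illustration, four levels.** A simulation of 200,000 patients assumed equally frequent levels and a marker unrelated to later severity. Each level raised the marker by d SD in the share s of patients sampled after reaching it. The table gives the AUC for the upper two levels against the lower two.

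| s | d = 0.25 | d = 0.5 | d = 1.0 |
|---|---|---|---|
| 0 | 0.50 | 0.50 | 0.50 |
| 25% | 0.53 | 0.56 | 0.59 |
| 50% | 0.57 | 0.62 | 0.68 |
| 100% | 0.64 | 0.75 | 0.90 |

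**Effect on the 400.** Assume equal levels again, 100 each. If a share s of the top level is already there when first sampled, 100 × (1 − s) of that level remain for prediction: 75 at s = 25% and 50 at s = 50%. The total falls to 375 and 350, and the top level to 75/5 = 15 and 50/5 = 10 per predictor, against the planned 20. The protocol does not give the true share.

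**The case against.** The strongest reply is that which sample supplies a covariate, when the outcome is graded and who enters the analysis set are ordinary content of a statistical analysis plan, which is not at hand. Enrolling intensive-care patients does not by itself put them in the predictive model. Much of this stands: the protocol fixes no wrong time order, and a later plan could choose the earliest sample. But that plan could not supply a pre-severity sample for someone first bled when ventilated, and the protocol itself sizes the model on all infected individuals. The gap is therefore partly one of design and counting.

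Three stronger readings are tempting, and the document does not support them.
- A reader might infer that the pneumonia-triggered sample feeds the model. No section says so; none excludes it either. The intensive-care route carries the point without it.
- A reader might infer that finding at-risk people through immune markers is the aim of the study. The Overall Purpose/objectives section seeks preliminary data on prevalence and on factors bearing on severity, treats the immune response as something to describe during infection and recovery, and frames objective (d) as exploring relationships. For those association aims, sampling during severe disease is appropriate. The point reaches only the predictive model.
- A reader might infer that the model is bound to predict severity from its own consequence. Usable early samples exist: non-hospitalised and non-symptomatic patients are eligible, and staff are sampled at recruitment regardless of symptoms. One of six candidate predictors is in question, and the share sampled late is unknown.

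It is also fair to say that the AUC figures use no input from the protocol and describe a single marker, not the planned multi-predictor model.

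**Conclusion.** The point holds in a limited form. For the immune response measure, the severity model could partly reflect the consequence of severe disease, because some enrolled patients can have reached their severity level before the first sample and nothing in the stated model separates them. Restricting the predictor to the recruitment sample would not be enough.

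The size cannot be derived from the protocol. With a null marker shifted by 1 SD, apparent AUC is 0.63 if half of severe patients are sampled late and 0.76 if all are. At a late share of 25% the four-level simulation gives only 0.53 to 0.59. These figures show how an artefact could arise and are not estimates for this study. The other candidate predictors, the association analyses and the prevalence objectives are not called into question. This is a worthwhile correction to one model, not a flaw that undermines the study.

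**What to change.** Amend the severity-model paragraph of the Statistical Analysis section as follows:
- Set the prediction time at the recruitment sample.
- Take the immune predictor only from that sample, and not from the 14–28 day or pneumonia-triggered samples.
- Record the severity level at that sample, and define the outcome as the highest level reached afterwards.
- Adjust for severity level at sampling, or model progression beyond it. Excluding only top-level patients would leave the same problem at the intermediate levels, because a patient's later maximum cannot be below the current level.
- Exclude from the predictive model those already at the top level when first sampled. Report immune markers in them, and from all later samples, as association only.
- Restate the 400 as the number eligible for the predictive model.

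No new samples or visits are needed. The cost goes beyond wording: fewer patients inform the model, and the loss falls on the top level. Severity level at sampling must also be taken from care records, since the data-collection section names time to admission but not the date on which each severity level was reached.

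### The severity model's 20 events per predictor counts five predictors where six candidates are named; for six, with four equal levels, 400 analysed gives 16.7

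*Protocol*

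**What the plan says.** The second part of the protocol's Statistical Analysis section plans a multi-predictor regression model for COVID-19 severity, "with age, comorbidity, gender, immune response measure, viral strain, and host genetics as candidate predictor variables". That list has six entries. The sentence continues: "although some of them may turn out to be non-significant predictors. Therefore, we anticipate 5-predictor models to be constructed from the dataset". The sample size follows as "4 levels of severity measure X 20 events per predictor X 5 predictors = 400".

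The protocol then moves from 400 to 500: "Allowing for some loss of sample due to follow up we estimate that recruiting a sample of" 500 "total infected individuals from both settings is sufficient for our study". No loss rate is given at this point. Of the resulting 20 EPV it says that "it is well above the minimum 10 EPV recommended for building predictive models".

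Two other points bear on the figure. The protocol gives no expected distribution of participants over the four severity levels. The section on hospital and nursing home patient recruitment plans 700 COVID-19 positive patients, a number that the model calculation does not use.

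**The concern.** EPV guards against overfitting. What matters for that purpose is how many parameters the data are allowed to choose among, not how many remain in the final model. The protocol's reason for using five is that "although some of them may turn out to be non-significant predictors", which can be learned only by testing all six on the same participants. The selection step uses the same events, so the dropped candidate belongs in the count.

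The formula also carries an unstated assumption. Multiplying by four gives 20 per predictor in every level only if the four levels are of equal size.

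What is at stake is the accuracy of the justification. The EPV is the support offered in that section for calling 500 infected participants enough for the severity model, and it is stated more favourably than the protocol's own formula gives for its own candidate list.

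**Working it through.** **Inputs, all from the Statistical Analysis section unless noted**
- Severity levels: 4
- Target EPV: 20; minimum cited: 10
- Predictors counted: 5; candidates named: 6
- Analysed: 400; recruited: 500
- Patients planned in the recruitment section: 700
- Loss rate: not stated for this model. The step from 500 to 400 implies (500 − 400)/500 = 20%.

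**The plan's own figure.** N = levels × EPV × predictors = 4 × 20 × 5 = 400. This reproduces exactly, and 400/(1 − 0.20) = 500.

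**EPV per level.** With equal levels and one parameter per candidate, EPV = N/4/k:

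| Analysed | k = 5 | k = 6 |
|---|---|---|
| 400 | 400/4/5 = 20.0 | 400/4/6 = 16.7 |
| 500 (no loss) | 500/4/5 = 25.0 | 500/4/6 = 20.8 |

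**Number needed for 20 EPV with six candidates.** 4 × 20 × 6 = 480 analysed.

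**Using the 700 patients instead.** With an assumed 20% loss, 700 × 0.80 = 560 analysed, and 560/4/6 = 23.3. This requires all of them to be infected and to enter the model.

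**Sensitivity to the equal-levels assumption.** On a per-level count, EPV in the smallest level = N × share/k. The shares below are assumptions, because the protocol gives none. At 400 analysed:

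| Share of smallest level | k = 5 | k = 6 |
|---|---|---|
| 25% (equal levels) | 20.0 | 16.7 |
| 20% | 16.0 | 13.3 |
| 15% | 12.0 | 10.0 |
| 10% | 8.0 | 6.7 |

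The smallest level stays at 10 or more if its share is at least 60/400 = 15% with six candidates, or 50/400 = 12.5% with five.

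**If one proportional-odds model is fitted.** With equal levels, the effective sample size at 400 is 400 × (1 − 4 × 0.25³) = 375, or 375/6 = 62.5 per predictor. The smallest-level limit does not then apply.

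**The case against.** The strongest reply is that nothing of consequence changes. The multiplication is correct, and 16.7 is still 67% above the cited minimum of 10. The protocol is also open about its reasoning: it lists all six candidates and says why it expects five in the final model. This stands as a limit on the size of the point. It does not make five the right divisor.

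A reader might infer that the model has too few events, below 10 per predictor. The documents do not support that. It would take an uneven severity split combined with per-level counting, or several parameters per candidate (at 400 with equal levels, 10.0 is reached only at ten parameters). The protocol fixes none of the split, the model type or the coding, and the last two can properly be left to the SAP. Under a proportional-odds model 400 would be ample for six single-parameter predictors.

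A reader might also infer that the study can lose only 4% of its participants, since (500 − 480)/500 = 4%. That treats 500 as all that is available. From the 700 planned patients, 480 would tolerate a loss of (700 − 480)/700 = 31%. There are limits on this reply too: the inclusion criteria also admit suspected cases, so not all 700 may be infected, and the model calculation does not cite the 700.

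Finally, the 20% loss is inferred. The protocol attributes the loss to follow-up, and data collected at recruitment may still be usable for participants lost later. If all 500 are retained, six candidates give 20.8 and the stated 20 is met.

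**Conclusion.** The point holds as a minor correction. For the six candidates it names, the protocol's formula gives 16.7 EPV per level at 400 analysed, not 20, and 20 EPV requires 480. These figures assume four equal severity levels and one parameter per candidate, so six is the lowest defensible count.

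The finding goes no further than that. The claim of exceeding 10 is not shown to be false; it depends on equal levels when EPV is counted by level. The calculation does not show that 500 is inadequate or that more participants are needed.

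**What to change.** Restate the EPV passage so that it:

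1. Counts all candidate parameters, at least six, and reports 16.7 per level at 400 analysed and 20.8 if all 500 are retained.
2. Says that the formula assumes four equal severity levels.
3. Either keeps 500 with the lower EPV, or ties the calculation to the 700 patients in the recruitment section: 560 analysed after an assumed 20% loss, giving 23.3 if all are infected and enter the model.
4. Keeps the comparison with 10 EPV, marked as conditional on equal levels.

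The model type, the coding of candidates and the selection method can stay in the SAP. The cost is a few sentences of wording, with no added enrolment; if 500 is kept, the stated EPV becomes slightly less favourable.
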